# LIST OF ABBREVIATIONS

ADA anti-drug antibodies ADR adverse drug reaction

AE adverse event

AESI adverse event of special interest

AIDS acquired immunodeficiency syndrome

ALT alanine aminotransferase

ASH American Society of Hematology

CI confidence interval

CIOMS Council for International Organizations of Medical Sciences

CRO contract research organization

CTCAE common terminology criteria for adverse events

CTR clinical trial report

DSMB data safety monitoring board

ECG electrocardiogram

eCRF electronic case report form EDC electronic data capture

FAS full analysis set

Fc crystallized fragment

FcRn neonatal crystallized fragment receptor

FSH follicle-stimulating hormone

GCP good clinical practice
HBV hepatitis B virus
HCV hepatitis C virus

HIV human immunodeficiency virus

ICF informed consent form

ICH International Council for Harmonisation of Technical Requirements

for Pharmaceuticals for Human Use

ID identification number

IEC Independent Ethics Committee

Ig immunoglobulin

IMP investigational medicinal product

IND investigational new drug

IRB Institutional Review Board
IRT interactive response technology
ITP immune thrombocytopenia

IUD intrauterine device

IV intravenous

IVIg immunoglobulins given intravenously

LS least square

MG myasthenia gravis

NCI National Cancer Institute

OR odds ratio

PD pharmacodynamic
PK pharmacokinetics
PLEX plasmapheresis
PP per protocol

PRO patient-reported outcomes q2w biweekly/every other week

QoL quality-of-life

SAE serious adverse event SAP statistical analysis plan

SC subcutaneous

SoA schedule of assessments
SOP standard operating procedure

TEAE treatment-emergent adverse event TPO-RA thrombopoietin receptor agonist

US United States

WHO World Health Organization

WHO-DD World Health Organization Drug Dictionary

# **DEFINITION OF TERMS**

#### **Blinding:**

A procedure in which 1 or more parties to the trial are kept unaware of the treatment assignment in order to reduce the risk of biased trial outcomes. The level of blinding is maintained throughout the conduct of the trial, and only when the data are cleaned to an acceptable level of quality will appropriate personnel be unblinded or when required in case of a (serious) adverse event ([S]AE). In a double-blind trial, the patient, the investigator, site staff, and sponsor staff who are involved in the treatment or clinical evaluation of the patients and the review or analysis of data are all unaware of the treatment assignment.

#### **Childbearing potential:**

Women of childbearing potential are defined as all female participants unless they are postmenopausal (defined by continuous amenorrhea) for at least 1 year with a follicle-stimulating hormone (FSH) of >40 IU/L or are surgically sterile (ie, who had a hysterectomy, a bilateral salpingectomy, a bilateral oophorectomy, or have current documented tubal ligation or any other permanent female sterilization procedure). Determination of FSH levels can be used to confirm postmenopausal status in amenorrheic patients not on hormonal replacement therapy.

# Council for International Organizations of Medical Sciences:

The Council for International Organizations of Medical Sciences (CIOMS) is an international, non-governmental, non-profit organization established jointly by the World Health Organization (WHO) and United Nations Educational, Scientific and Cultural Organization in 1949. They provide a set of ethical principles regarding human experimentations, including International Reporting of adverse drug reactions (ADRs) and International Reporting of Periodic Drug-Safety Update Summaries.

The CIOMS form provides a standardized format for the reporting of suspected adverse reactions to any particular medicinal product and is the accepted and widely used format for reporting suspected ADR/suspected unexpected serious adverse reaction in clinical trials.

# **Contract Research Organization:**

A person, or a group of persons (commercial, academic, or other), who as an independent contractor with argenx BVBA, assume(s) 1 or more obligations of argenx BVBA, eg, development of a protocol, selection and/or monitoring of investigators, evaluation of reports, preparation of materials to be submitted to regulatory authorities.

**Database lock:** 

An action taken to prevent further changes to a trial database. A database is locked after review, query resolution, data cleaning and determination that it is ready for analysis.

**Data Safety Monitoring Board:** 

Independent group of experts that advises and whose responsibilities are to periodically review and evaluate the accumulated trial data for participant safety, trial conduct and progress and, when appropriate, efficacy, and to make recommendation to the sponsor concerning the continuation, modification or termination of the trial.

Eligible:

Qualified for randomization into the trial based upon strict adherence to inclusion/exclusion criteria.

**Good Clinical Practice:** 

A standard for the design, conduct, performance, monitoring, auditing, recording, analyses, and reporting of clinical trials that provides assurance that the data and reported results are credible and accurate, and that the rights, integrity, and confidentiality of trial patients are protected. (International Council for Harmonisation of Technical Requirements for Human Use [ICH] E6).

Institutional Review
Board/Independent Ethics
Committee:

An independent body (a review board or a committee, institutional, regional, national, or supranational), constituted of medical professionals and non-medical members, whose responsibility it is to ensure the protection of the rights, safety and well-being of human subjects involved in a trial and to provide public assurance of that protection, by, among other things, reviewing and approving / providing favorable opinion on, the trial protocol, the suitability of the investigator(s), facilities, and the methods and material to be used in obtaining and documenting informed consent of the trial subjects.

**Informed Consent/ Informed Consent Form:** 

A process by which a clinical investigation participant voluntarily confirms his or her willingness to participate in a particular clinical trial, after having been informed of all aspects of the trial that are relevant to the participant's decision to participate. Informed consent is documented by means of a dated and signed informed consent form (ICF).

International Council for Harmonisation: The ICH is a project that brings together the regulatory authorities of Europe, Japan, and the United States (US), and experts from the pharmaceutical industry in the 3 regions to discuss scientific and technical aspects of pharmaceutical product registration.

**Investigational Medicinal Product:** 

A pharmaceutical form of an active ingredient or placebo being tested or used as a reference in a clinical trial, including a product with a marketing authorization when used in a way different from the approved form, or when used for an unapproved indication, or when used to gain further information about an approved use.

**Protocol amendment:** A written description of a change(s) to or formal clarification

of a protocol.

**Randomization:** Process of random attribution of treatment to subjects in

order to reduce bias of selection.

**Treatment:** Term used throughout the clinical trial to denote a set of

investigational product(s) or marketed product(s) or placebo

intended to be administered to a subject.

#### 1. INTRODUCTION

# 1.1. Background Information

Efgartigimod (ARGX-113) is a modified human immunoglobulin (Ig) G1-derived crystallized fragment (Fc) of the za allotype that binds with nanomolar affinity to the human neonatal crystallized fragment receptor (FcRn). Efgartigimod encompasses IgG1 residues D221-K447 (EU numbering scheme) and has been modified with the so-called ABDEGTM technology (ABDEGTM = antibody that enhances IgG degradation) to increase its affinity for FcRn at both physiological and acidic pH. The increased affinity for FcRn of efgartigimod at both acidic and physiological pH results in a blockage of FcRn-mediated recycling of IgGs.

Given the essential role of the FcRn receptor in IgG homeostasis, inhibiting this FcRn function, as is achieved by efgartigimod, leads to rapid degradation of all IgGs, including disease-associated autoantibodies of the IgG isotype. This approach is thought to result in alleviation of signs and symptoms in IgG-driven autoimmune diseases.

The safety, tolerability, pharmacokinetics (PK), and pharmacodynamics (PD) of intravenous (IV) administrations of efgartigimod have been investigated in a first-in-human study in healthy adult subjects. A second study in healthy adult subjects investigated the bioavailability, safety, tolerability, immunogenicity, PK, and PD of a subcutaneous (SC) administration of efgartigimod and evaluated the reduction of the IV infusion time from 2 hours to 1 hour.

Phase 2 trials in immune thrombocytopenia (ITP) and myasthenia gravis (MG) have indicated that efgartigimod administered by IV infusion is well tolerated; induces a specific, rapid, and profound PD effect (ie, reduction in IgG levels, including autoantibody levels); and is associated with improvement in clinical signs and symptoms in ITP and MG patients, separately (see Section 1.3). Additionally, the safety and tolerability of efgartigimod is currently being evaluated for the treatment of patients with pemphigus in a phase 2 trial.

Primary ITP is an acquired autoimmune bleeding disorder characterized by an isolated low platelet count (<100×10^9/L) in the absence of other causes or disorders associated with thrombocytopenia. Prevalence of ITP is estimated at 9.5 per 100 000 adults, and incidence rates have been reported at 3.3 per 100 000 adults/year. In adults, the prevalence of ITP increases with age. Adult ITP can persist for years. Even with best available care, patients rarely achieve long-term remission, and often require multiple treatment options. ITP can be described based on the duration of disease: newly diagnosed (within 3 months of diagnosis), persistent (between 3 and 12 months from diagnosis), and chronic (lasting for more than 12 months).

In primary ITP, platelet destruction and impaired platelet production are driven by IgG autoantibodies targeting surface receptors on platelets and their progenitor cells. The resulting, often severe, thrombocytopenia may be accompanied by a variety of symptoms including evidence of bleeding in the skin and mucosa, and risk of serious intracranial and

argenx BVBA Confidential Page **36** of **162** 

gastrointestinal bleeding complications. The highest concern is the risk of significant bleeding, such as intracranial hemorrhage. The 5-year fatal hemorrhage rate is higher in older patients with ITP, especially in those with comorbid conditions. Other clinically significant concerns include complications from internal bleeding and elevated risk of arterial thrombosis and venous thromboembolism. Immune thrombocytopenia is also associated with fatigue, reported in up to 39% of adults with ITP, as well as impaired quality-of-life (QoL). These comorbidities interfere with work and social life, which can lead to feelings of embarrassment, isolation, and sexual inadequacy.

Several drugs and medical procedures are routinely used in the management of ITP. First-line therapy in primary ITP is corticosteroids, as well as immunoglobulins given intravenously (IVIg) and anti-D. Second-line treatments include broad immunosuppressants and thrombopoietin receptor agonists (TPO-RAs). There is limited evidence to guide the use of these treatments, as described in the American Society of Hematology (ASH) guidelines. There is no evidence to guide a sequence of treatments for patients who have recurrent or persistent thrombocytopenia associated with bleeding after an initial treatment course with corticosteroids (or IVIg or anti-D). Patients may cycle through different treatment regimens seeking any that is efficacious and tolerable. Immune thrombocytopenia remains a chronic disease despite the availability of several treatments with differing mechanisms of action. According to the ASH ITP guidelines only splenectomy has provided evidence of remission at 1 year. Additionally, a significant proportion of patients develop resistance to treatment. Furthermore, existing treatments are associated with burdensome side-effects limiting their use (eg, long-term steroid treatment) and/or concern about use in patient populations (eg, TPO-RAs in patients with elevated cardiovascular risk).

Targeted and selective IgG reduction, as achieved by efgartigimod, has the potential as an effective new treatment in ITP seen the central role of IgG autoantibodies in the pathophysiology of ITP. It represents a novel mechanism of action distinct from that of other existing treatments which are either broadly immunosuppressive or stimulate thrombopoiesis.

#### 1.2. Benefit-Risk Assessment

Efgartigimod has been shown to effectively reduce IgG antibodies in several clinical trials, including healthy volunteers, patients with MG, and with ITP.

More specifically, a phase 2 trial (ARGX-113-1603) in patients with ITP enrolled a patient population who was predominantly refractory to previous lines of ITP therapy, with the majority of patients having long-standing disease, prior ITP treatment exposure and approximately half with baseline platelet count of  $<15\times10^9/L$ .

Efgartigimod resulted in a rapid and marked reduction of IgG antibodies (maximum mean reduction of 65%) and of all IgG subtypes.

argenx BVBA Confidential Page 37 of 162

Treatment with efgartigimod, whether 5 mg/kg or 10 mg/kg, was associated with an increase in platelet counts in more patients than occurred in the placebo group, with greater numerical separation from placebo as the platelet count threshold stringency was increased. Additional post hoc analyses further supported these observations, showing a longer duration of clinically meaningful effect and statistically significantly more active-treated patients achieving a platelet count of  $\geq 50 \times 10^9/L$  for more than 10 cumulative days compared to the placebo group.

In each of the subgroups of patients based on ITP classification (newly diagnosed, persistent, or chronic ITP) or those with or without historical or concomitant use of TPO-RA, there were examples of efgartigimod-treated patients with an increase in platelet count.

In the open-label treatment period patients received 4 weekly infusions of efgartigimed 10 mg/kg, either as first exposure in patients who previously received placebo or retreatment with efgartigimed. In this part of the trial, the majority of patients (58%) had improved platelet counts.

Efgartigimod is under investigation in MG, another disease driven by IgG autoantibodies. In a phase 2 trial ARGX-113-1602, 4 weekly IV infusions of 10 mg/kg efgartigimod led to statistically significant improvements in clinical scales and were well tolerated. A phase 3 trial ARGX-113-1704 and accompanying open-label extension trial ARGX-113-1705 are ongoing in this indication.

In clinical trials to date, efgartigimod has been well tolerated in healthy adult subjects and patients with MG and ITP, separately: the majority of treatment-emergent AEs (TEAEs) were considered to be mild (grade 1) in severity. In the completed phase 1 trials ARGX-113-1501, ARGX-113-1702, and ARGX-113-1901 in healthy volunteers, and in the phase 2 trial ARGX-113-1602 in patients with MG, no grade ≥3 TEAEs were reported and no TEAE led to discontinuation. In the phase 2 trial ARGX-113-1603 in patients with ITP, 1 TEAE with grade 4 was reported (thrombocytopenia), considered unrelated to treatment, and led to treatment discontinuation.

No clinically significant changes in vital signs and/or electrocardiogram (ECG) findings have been observed in clinical trials to date.

Safety for use during pregnancy has not been established. Therefore, efgartigimed should not be administered to pregnant or lactating women.

Please refer to the current Investigator's Brochure for more information regarding the preclinical and clinical trials, and the potential risks and benefits of efgartigimod. In summary, the favorable balance between risks and anticipated efficacy/benefits supports the use of efgartigimod in clinical development.

#### 1.3. Trial Rationale

The proposed phase 3 trial aims to establish the efficacy, safety, and impact on patient-reported outcomes (PRO) of efgartigimod administered as IV infusions in adult patients with primary

argenx BVBA Confidential Page 38 of 162

ITP who have had an insufficient response or who are intolerant to existing ITP treatments, evidenced by a platelet count that is below the clinically accepted level for intervention ( $<30\times10^9/L$ ).

Patients classified as having persistent ITP (between 3 and 12 months since diagnosis) and chronic ITP (greater than 12 months since diagnosis) will be recruited. At the start of the trial, the patients are either on concurrent ITP treatment(s) and have received at least 1 prior therapy for ITP in the past, or the patients are not on treatment for ITP but have received at least 2 prior treatments for ITP.

Treatments for ITP are often used in combination and efgartigimed has the potential to be used in combination with other ITP therapies or offer a new stand-alone modality. Therefore, patients with and without concurrent ITP therapy will be enrolled. Experience to date of efgartigimed treatment in combination with steroids and immunosuppressants in phase 2 ITP and MG trials has not raised any safety concerns with these combinations of treatments.

This trial will utilize an IV dosing schedule aiming to maximize PD effect (ie, reduction of autoantibody levels) and seeking to result in an improvement in platelet count. In patients who achieve a prespecified threshold of maintained platelet count improvement, the frequency of efgartigimod administration will be altered (ie, increased or decreased) according to prespecified criteria, after which the frequency of administration will be unchanged for the last 7 weeks (visits 17 to 24) of trial treatment. Assessment of the dosing regimen as described in Section 5.4.1 will be applied. The aim is to achieve the maximum possible proportion of patients with a platelet count improvement and then assess whether this can be sustained in the last 5 weeks of trial treatment.

Based on the results of the phase 1 trial in healthy adult subjects, the phase 2 trial in patients with ITP, as well as the PK/PD modeling analysis, a dose of 10 mg/kg efgartigimod was selected as it is considered safe and well tolerated, achieved consistently a close to maximal IgG reduction (ie, 65-70%), and resulted in a clinical response (eg, increase in platelet count) in a significant proportion of patients. This dose is also being utilized in the ongoing phase 3 trials in MG (see Section 1.2).

A continuous dosing regimen of weekly or biweekly (q2w) IV infusions of 10 mg/kg efgartigimod is anticipated to be safe. In a long-term toxicity trial (26-weeks with 8-weeks recovery period), cynomolgus monkeys were dosed with weekly efgartigimod infusions of up to 100 mg/kg. The no observed adverse effect level was set at the highest administered dose of 100 mg/kg. The exposures achieved in this toxicity study were between 35.5 (female animals) and 40.8 (male animals) times the simulated area under the curve values in ITP patients using the clinical dose of 10 mg/kg.

argenx BVBA Confidential Page 39 of 162

### 2. TRIAL OBJECTIVES

## 2.1. Primary Objective

• To evaluate the efficacy of efgartigimod compared to placebo in achieving a sustained platelet count response in patients with primary chronic ITP, with a sustained platelet count response defined as platelet counts of at least 50×10^9/L for at least 4 of the 6 visits between week 19 and 24 of the trial\*.

# 2.2. Secondary Objectives

- To evaluate the efficacy of efgartigimod compared to placebo in overall platelet count response.
- To evaluate the safety and tolerability of efgartigimod administered IV weekly or q2w.
- To evaluate the incidence and severity of bleeding events while receiving treatment with efgartigimod compared to placebo.
- To evaluate the use of rescue treatment and changes in concurrent ITP therapy while receiving treatment with efgartigimod compared to placebo.
- To evaluate the effects of efgartigimod treatment on QoL measures and PRO compared to placebo.
- To assess the immunogenicity of efgartigimod.
- To assess the PK of efgartigimod.
- To assess the PD effects of efgartigimod.

# 2.3. Exploratory Objective

argenx BVBA Confidential Page 40 of 162

\* "week" instead of "visits" are used in the endpoints, ensuring that the platelet count of the EoT visit is regarded as week 24 platelet count. (eg, platelet count after 19 weeks of treatment corresponds with platelet count of visit 20).

### 3. TRIAL ENDPOINTS

# 3.1. Primary Endpoint

• Proportion of patients with chronic ITP with a sustained platelet count response defined as achieving platelet counts of at least 50×10^9/L for at least 4 of the 6 visits between week 19 and 24 of the trial.

Patients who discontinue treatment prior to visit 24 due to lack of efficacy (eg, more than 3 occurrences of rescue therapy) or due to an AE, and who have not achieved sustained platelet count response between week 19 and 24, are considered non-responders. Patients who receive rescue therapy at week 12 or later, or for whom dose and/or frequency of concurrent ITP therapies have increased at week 12 or later, are also considered non-responders.

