### 4.4.2. Early Discontinuation From Treatment

Early discontinuation from treatment means that the patient stops receiving the ongoing IMP treatment and does not restart IMP treatment, however, informed consent is not withdrawn. These patients will continue the weekly trial visits as specified in the SoA (Table 1) without IMP-related assessments.

Patients **must** be discontinued early from **treatment** in the following circumstances:

- on the request of the sponsor (eg, following data safety monitoring board [DSMB] advice, see Section 7.3.5)
- patient has missed more than 2 consecutive scheduled doses of IMP treatment
- patient has received more than 3 occurrences of rescue therapy

Patients who complete the 24-week trial period but who do not enter the open-label extension trial ARGX-113-1803, or patients who discontinue the trial early, with the exception of patients who withdraw their consent, will be followed for 4 weeks for ongoing safety and efficacy monitoring.

argenx BVBA Confidential Page 52 of 162

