# 8.4.1. Primary Endpoint Analysis

# Definition of the estimand for the primary endpoint

- Population: adult patients with chronic ITP, having an average platelet count of <30×10^9/L, and, at the start of the trial, either being on concurrent ITP treatment(s) and having received at least 1 prior therapy for ITP in the past, or not being on treatment for ITP but having received at least 2 prior treatments for ITP
- Variable: sustained platelet count response defined as achieving platelet counts of at least  $50 \times 10^9$ /L for at least 4 of the 6 visits between week 19 and 24 of the trial
- Main intercurrent events:
  - i. early discontinuation of treatment (prior to visit 24) due to lack of efficacy (eg, more than 3 occurrences of rescue therapy) or due to an AE
  - ii. initiation of rescue therapy at week 12 or later
  - iii. increase of dose and/or frequency of concurrent ITP therapies at week 12 or later
- Population-level summary: proportion of patients with sustained platelet count response

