# Handling of main intercurrent events

A composite strategy approach will be taken to address the main intercurrent events described above. This implies that patients who discontinue treatment prior to visit 24 due to lack of efficacy (eg, more than 3 occurrences of rescue therapy) or due to an AE, as well as patients who receive rescue therapy at week 12 or later, or for whom dose and/or frequency of concurrent ITP therapies have increased at week 12 or later, will be considered non-responders for the primary endpoint analysis.

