1.2 STUDY ENDPOINTS

1.2.1 Primary endpoint

The primary endpoint is the proportion of patients with chronic ITP with a sustained platelet count response defined as achieving platelet counts of at least 50×10^9 /L for at least 4 of the 6 visits between week 19 and 24 of the study.

Patients who discontinue treatment prior to visit 24 due to lack of efficacy (e.g. more than 3 occurrences of rescue therapy) or due to an AE, and who have not achieved sustained platelet count response between week 19 and 24, are considered non-responders. Patients who receive rescue therapy at week 12 or later, or for whom dose and/or frequency of concurrent ITP therapies have increased at week 12 or later, are also considered non-responders.

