4.1.2.1 PRIMARY ENDPOINT

The primary endpoint is the proportion of patients with a sustained platelet count response (week 19 - 24) within the adult population with chronic ITP.

A patient is considered a responder, i.e. has a sustained platelet count response, if he/she shows platelet counts of at least 50×10^9 /L for at least 4 of the 6 analysis visits between weeks 19 and 24 of the study. ($\geq 50 \times 10^9$ /L prim resp).

The main analysis on the primary endpoint will use the 'composite variable strategy' in case of main intercurrent events using the Cochran-Mantel-Haenszel test (see also section 4.1.3.2). This strategy implies that when a main intercurrent event occurs, a patient is considered a non-responder, if the patient has not achieved sustained platelet count response before the occurrence of the main intercurrent event. This happens in the following situations:

- early discontinuation of treatment (prior to week 24) due to lack of efficacy (DSDECOD = "Lack of efficacy") or due to an AE
- initiation of rescue therapy at week 12 or later: relative day of start date of rescue medication ≥ target ADY of analysis visit corresponding to Week 12

SGS	Statistical Analysis Plan	
ARGX-113-1801	Final analysis	Final 1.0 of 28MAR2022

- increase of dose and/or frequency of concurrent ITP therapies or start of a new concurrent ITP therapy at week 12 or later:
 - (if start date concurrent ITP therapy ≥ target ADY of analysis visit corresponding to Week 12) and (dose > previous dose of the specific ITP therapy OR frequency > previous frequency of the specific ITP therapy)

AND

(if start date concurrent ITP therapy ≥ target ADY of analysis visit corresponding to Week 12) and (dose > dose of the specific ITP therapy at baseline OR frequency > frequency of the specific ITP therapy at baseline)

OR

• new ITP therapy

Note: if for frequency a change is detected, but it is not clear whether a real increase has taken place, it will be considered worse-case and analysed as increase (e.g.: Baseline value 'QD' changed to e.g. 'at will', 'as needed'; Baseline value 'As needed' changed to e.g. 'QD, ', 'continuous').

Missing values for reasons other than the main intercurrent events, will be imputed as described in section 4.1.2.5 (approach 1).

A complementary analysis for this primary analysis will use the 'treatment policy strategy' where these main intercurrent events are handled differently.

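### The protocol's estimand section and the SAP score patients with a main intercurrent event differently on the primary endpoint: unconditional non-response in one, an exemption for earlier responders in the other

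*Protocol*

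**What the plan says.** The rule for main intercurrent events appears in three forms.

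- **Protocol 3.1** (repeated in the synopsis and 4.2): patients who stop treatment before visit 24 for lack of efficacy or "due to an AE, and who have not achieved sustained platelet count response between week 19 and 24, are considered non-responders". A second sentence makes rescue, or an increase in concurrent ITP therapy, at week 12 or later a non-response with no exception. SAP 1.2.1 repeats both sentences, including "and who have not achieved sustained platelet count response between week 19 and 24, are considered non-responders".
- **Protocol 8.4.1, handling of main intercurrent events**: the strategy is composite. "This implies that patients who discontinue treatment prior to visit 24 due to lack of efficacy" or an AE, together with patients who have rescue or increased concurrent therapy at week 12 or later, "will be considered non-responders for the primary endpoint analysis". No exception is given for any of the three events.
- **SAP 4.1.2.1**: the composite strategy is stated with a condition on timing: "a patient is considered a non-responder, if the patient has not achieved sustained platelet count response before the occurrence of the main intercurrent event". The three event types are then listed under this condition.

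The time limit for a treatment stop is also worded differently. The protocol's estimand has "early discontinuation of treatment (prior to visit 24) due to lack of efficacy"; SAP 4.1.2.1 has "early discontinuation of treatment (prior to week 24) due to lack of efficacy".

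SAP 6.1, which lists changes not covered by protocol amendments, mentions none of this. SAP 4.1.2.2 applies the 4.1.2.1 strategy to key secondary endpoints 2 and 4.

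**The concern.** This is the gatekeeping endpoint. Its estimand rests on a composite strategy, and the documents do not agree on which patients the composite turns into non-responders. A composite that spares patients who responded before the event answers a different question from one that does not. If the conflict is settled only once results are known, the choice can be challenged as driven by outcome. The conflict also carries into two further alpha-controlled endpoints.

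**Working it through.** No stated figure is at issue. The check applies each rule to the same patients.

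**Inputs.** The response window is analysis weeks 19 to 24, with 4 of 6 counts of at least 50×10⁹/L required (Protocol 3.1, SAP 4.1.2.1). From the schedule of assessments and SAP Table 3, week 19 is day 134 (visit 20), week 22 is day 155 (visit 23), week 23 is day 162 (visit 24) and week 24 is day 169 (End-of-Treatment). After stopping IMP, "These patients will continue the weekly trial visits as specified in the SoA (Table 1) without IMP-related assessments" (Protocol 4.4.2). SAP 4.1.2 uses treatment-phase counts, and that phase runs to End-of-Treatment for patients who stay in the trial (SAP Table 2).

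**Three patients**, each with counts of at least 50 at weeks 19 to 22 and below 50 at weeks 23 and 24 (R = responder, NR = non-responder):

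| Event | 3.1 and SAP 1.2.1, read literally | The same, read as by the time of stopping | Protocol 8.4.1 | SAP 4.1.2.1 |
|---|---|---|---|---|
| A. Stops for an AE after the day 155 count, before visit 24 | R | R | NR | R |
| B. Stops for an AE at week 15 | R | NR | NR | NR |
| C. Rescue after the week 22 count | NR | NR | NR | R |

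Patient A separates 8.4.1 from the rest on either reading of 3.1, and needs no count taken after the stop. Patient C separates SAP 4.1.2.1 from everything else, including SAP 1.2.1. Patient B is discordant only on the literal reading of 3.1.

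**The literal reading of 3.1.** A patient who has not met 4 of 6 over the whole window is a non-responder already, so the treatment-stop clause reclassifies nobody.

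**How many count patterns are exposed.** Six counts give 2⁶ = 64 patterns. Those meeting 4 of 6 number C(6,4) + C(6,5) + C(6,6) = 15 + 6 + 1 = 22. Let k be the number of window counts taken before the event. SAP 4.1.2.1 exempts a pattern if at least 4 of the first k counts qualify:

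- k = 0 to 3: no pattern is exempt, so the SAP and 8.4.1 agree.
- k = 4: 1 × 2² = 4 patterns are exempt.
- k = 5: (5 + 1) × 2 = 12 patterns are exempt.

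Protocol 8.4.1 exempts none, so it disagrees with the SAP on 4 patterns at k = 4 and on 12 at k = 5. On schedule, a stop before visit 24 follows at most four window counts (weeks 19 to 22), so k = 5 concerns mainly rescue and increased concurrent therapy, which have no upper time limit. Read literally, 3.1 keeps all 22 patterns as responders after a treatment stop. It therefore disagrees with 8.4.1 on 22 at any stop time, and with the SAP on 22 for k up to 3 and on 22 − 4 = 18 at k = 4. These are counts of patterns, not probabilities.

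**Size per patient.** With 117 patients at 2:1, the arms hold about 78 and 39. One reclassified patient moves the rate by 1/78 = 1.3 points or 1/39 = 2.6 points.

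**Power.** The planned rates are redacted, so three pairs giving about 90% power were assumed (placebo vs efgartigimod). Power is for a two-sided 5% pooled two-proportion test by exact binomial enumeration, unstratified:

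| Assumed rates | No change | 2 points off efgartigimod only | 2 points off both arms |
|---|---|---|---|
| 3% vs 24% | 0.911 | 0.858 | 0.968 |
| 5% vs 28% | 0.906 | 0.857 | 0.947 |
| 10% vs 37% | 0.916 | 0.875 | 0.936 |

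The sign depends on which arm loses responders, and the documents do not say.

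**The case against.** The strongest reply is that there is one operative derivation. Protocol section 8 leaves detail and changes to the SAP, SAP 4.1.2.1 is the version that can be programmed, and SAP 4.1.3.2 refers back to it. Protocol 3.1 can fairly be read as not having responded by the time of stopping. That gives its clause some effect and makes it agree with the SAP for treatment stops, leaving 8.4.1 as the outlier for that event.

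The affected group is also narrow. The documents' example of lack of efficacy is more than three rescue occurrences, and any rescue from week 12 is itself a main intercurrent event. Several safety reasons end trial participation rather than treatment alone (Protocol 4.4.1), so weekly counts stop, and missing counts then default to below 50 (SAP 4.1.2.5). Protocol 4.2 describes the phase 2 responses as transient, which argues against many sustained responders off treatment. An increase under the insufficient-response rule requires four weeks with no count of 30×10⁹/L or more, which cannot follow four qualifying window counts before week 24; label-based TPO-RA or fostamatinib changes remain possible. Finally, a treatment-policy analysis is planned and the events will be tabulated and listed.

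Most of this stands as a limit on size. It does not remove the conflict. Section 8 expects changes to be stated in the SAP, and SAP 6.1 is silent. The charitable reading of 3.1 still contradicts 8.4.1 (patient A). For rescue and increased therapy, SAP 1.2.1 and SAP 4.1.2.1 disagree on any reading (patient C). The treatment-policy analysis lifts the composite for all events at once, so it does not show the effect of the exemption.

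**Conclusion.** The composite rule for the primary endpoint is inconsistent in the current text and should be reconciled. The firm conflict is between Protocol 8.4.1, which is unconditional for all three events, and SAP 4.1.2.1, which exempts earlier responders for all three. The exception in Protocol 3.1 and SAP 1.2.1 covers treatment stops only, and it contradicts 8.4.1 however it is read.

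The size is 1.3 or 2.6 points per reclassified patient, assuming arms of 78 and 39. The number of such patients cannot be derived and is probably small.

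A reader might infer three stronger points that the documents do not support:

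- **Three distinct rules for treatment stops.** This holds only on the literal reading of 3.1; otherwise there are two.
- **A loss of power.** This requires unsourced stopping and response rates and removal of responders from efgartigimod alone. Removing them equally from both arms raises power in the illustration.
- **A material difference between visit 24 and week 24.** No dose is scheduled after visit 24, so almost no treatment stop can fall between the two. This is a matter of wording.

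**What to change.** Before unblinding, state one scoring rule for all three intercurrent events, in identical words, in the synopsis, Protocol 3.1, 4.2 and 8.4.1, and SAP 1.2.1 and 4.1.2.1. Carry it to key secondary endpoints 2 and 4. Two routes are open:

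- **Unconditional composite, as in 8.4.1.** Remove the SAP exemption for response before the event, and remove the treatment-stop clause from 3.1 and its repeats.
- **Exemption, as in SAP 4.1.2.1.** Write it into 8.4.1 and 3.1 and their repeats for all three events, with the timing explicit, and list it in SAP 6.1.

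Report the rule not chosen as a sensitivity analysis, and use one cut-off term, visit 24 or week 24, throughout. Correcting only the treatment-stop clause would leave the conflict over rescue and increased concurrent therapy.

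The cost is a SAP revision, a protocol clarification and one extra analysis, with no new data. Protocol Appendix 5 attributes the treatment-stop sentence to an FDA request, so removing its clause should be raised with the agency.
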